#### **Patient and Disease Characteristics**

2. Documentation of PH1 as determined by genetic analysis prior to initial dosing.
3. Urinary oxalate:creatinine ratio greater than the upper limit of normal based on age on at least 2 of 3 single-void collections during screening.
4. If taking therapeutic vitamin B6 (pyridoxine), must have been on stable regimen for at least 90 days before screening, and is able to remain on this stable regimen until at least the Month 6 visit. Dose adjustments for interval weight gain are acceptable.

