4. PATIENT POPULATION

4.1. Patient Definitions

The populations (analysis sets) are defined as follows:

- Safety Analysis Set: All patients who received any amount of lumasiran during study.
- Efficacy Analysis Set: All patients who received any amount of lumasiran and have at least one valid spot urinary UOx:Cr ratio value at baseline and at least one valid spot urinary UOx:Cr ratio value from assessment(s) at Month 3 through Month 6.
- Primary Interim Efficacy Analysis Set: Among first 16 enrolled patients, all patients who received any amount of lumasiran and have at least one valid spot urinary UOx:Cr ratio value at baseline and at least one valid spot urinary UOx:Cr ratio value from assessment(s) at Month 3 through Month 6
- PK Analysis Set: All patients who received one full dose of lumasiran and have at least one postdose blood sample for PK parameters and have evaluable PK data.

The Safety Analysis Set will be used for safety analyses and sensitivity analysis of efficacy. The Efficacy Analysis Set will be used to evaluate efficacy endpoints. The PK Analysis Sets will be used to conduct PK analyses of plasma lumasiran concentrations.

The primary analysis period is defined as the time period from the date/time of the first lumasiran dose administration until either the date/time of lumasiran dose administration at Month 6 or the date of the Month 6 visit (Day 169) for patients who discontinued treatment prematurely. Primary analysis will be conducted using all data collected in the Primary Analysis Period. All data up to the dosing at the Month 6 visit will be included in the Primary Analysis Period.

The extension period starts after the date/time of lumasiran dose administration at Month 6 until the end of the study. Analysis of Extension Phase will focus on long-term efficacy of lumasiran.

Duration of Study is defined as the time period from on or after the first date/time of lumasiran dose until the end of the study. Analyses of Duration of Study will summarize secondary endpoints using data collected during the entire study period. These analyses focus on long-term efficacy and safety effects of lumasiran during both the primary analysis period and the extension period.

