5.4. Baseline Definitions

For spot urinary UOx:Cr ratio, baseline is defined as the mean of all spot urinary UOx:Cr ratio values collected prior to the first dose date/time of lumasiran. Baseline for all 24-hour urine parameters (i.e. 24-hour urinary oxalate corrected for BSA, etc) is defined as the median of all measurements collected prior to the first dose date/time of lumasiran. For all other PD parameters (i.e., plasma oxalate, etc.), baseline will use the mean of all measurements collected prior to the first dose date/time of lumasiran.

For other parameters, baseline is defined as the last non-missing value prior to the first dose date/time of lumasiran, unless otherwise specified. If multiple values are collected at a single visit (e.g. height, etc.), the mean of the values collected at the same visit will be used.

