7.3. Secondary Endpoints

For efficacy secondary endpoints, the Efficacy Analysis Set will be used; for PK secondary endpoints, the PK Analysis Set will be used.

Secondary endpoints in this study are as follows:

Extension Period (Month 6 to End of Study)

Percent change in spot urinary UOx:Cr ratio from baseline for all post-Month 6 visits will be summarized descriptively using the Efficacy Analysis Set. The analyses for 24-hour urinary oxalate corrected for BSA and 24-hour urinary UOx:Cr ratio will be carried out using Extension Period data as well.

Duration of Study (Baseline to End of Study)

Absolute changes in spot urinary UOx:Cr ratio and percent and absolute change in plasma oxalate from baseline using Efficacy Analysis Set will be performed similarly to primary analysis. In addition, percent and absolute change in plasma oxalate from baseline will also be analyzed using only patients in the Efficacy Analysis Set whose baseline plasma oxalate $\geq 1.5^*LLOQ$. LS means by postdose visits with corresponding SEM and 95% CIs will be displayed for the primary analysis period.

For continuous endpoints (including eGFR), descriptive statistics will be generated at each scheduled visit. Mean (+/- SEM) figures of actual values and changes from baseline will be plotted as well as individual spaghetti plots and listings. For binary endpoints, the number and associated percent of patients who met each threshold (e.g. $\leq ULN$ or $\leq 1.5 \times ULN$) at visits will be presented.

To demonstrate durability of the effect of lumasiran, for binary endpoints, (e.g. proportion of patients with spot urinary UOx:Cr ratio level $\leq ULN$ or $\leq 1.5 \times ULN$), tabular summaries of the number and percent of patients who met the threshold at post-baseline visits will be presented.

An analysis of the percentage of time that spot urinary UOx:Cr ratio is at or below the near-normalization threshold for the duration of study will be summarized. A patient is considered to have met the threshold if the spot urinary UOx:Cr ratio is $\leq 1.5 \times ULN$ at a post-baseline visit.

For each patient, the percentage of time that spot urinary UOx:Cr ratio is at or below the near-normalization threshold of $\leq 1.5 \times ULN$ will be calculated as follows:

$$\frac{\text{cumulative time at or below near normalization threshold}}{\text{cumulative time of valid assessments}} \times 100$$

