10.2.2. Effect of Age on Spot urinary UOx:Cr ratio in pediatric PH1 patients

There is limited longitudinal data of spot urinary UOx:Cr ratio in pediatric PH1 patients. Lieske reported spot urinary UOx:Cr ratio from 35 PH1 patients across ages from international registry of primary hyperoxaluria.[Lieske 2005] Of these patients, 15 children are under 7 years old, with 2 less than 2 years old.

To check whether similar decline is observed in PH1 patients as in selected studies involving unaffected children, single values of individual patient spot UOx:Cr (plotted in [Figure 1](#)) were read from Lieske's paper using Digitize (R package). Lieske's data are shown in [Figure 1](#) along with the reference curves for Lower limit of normal (LLN) and ULN identified by Matos' publication. All patients except for one patient under 1 year old had spot urinary UOx:Cr ratios above the Matos ULN.

Figure 1: Spot urinary UOx:Cr ratio (mmol/mmol) in children with PH1 based on [Lieske 2005] Data

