10.4. Normal Range Analysis

Normalization rate will be based on normal range analysis of PD parameters (i.e. spot urinary UOx:Cr ratio, 24-hour oxalate corrected BSA, etc.) from [REDACTED] healthy volunteer data. ULNs will be defined in the separate normal range report that will be finalized before database lock.

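### The counts at or below ULN and 1.5 × ULN take no account of baseline, although the entry rule admits children already at or below those limits

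*SAP*

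**What the plan says.** **Entry.** Protocol 4.1, criterion 3, asks for "Urinary oxalate:creatinine ratio greater than the upper limit of normal based on age on at least 2 of 3 single-void collections during screening". The third void may be normal, and no minimum is set for the mean.

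**Baseline.** SAP 5.4: "baseline is defined as the mean of all spot urinary UOx:Cr ratio values collected prior to the first dose date/time of lumasiran".

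**Denominator.** SAP 7.3: "For efficacy secondary endpoints, the Efficacy Analysis Set will be used". Under SAP 4.1 that set needs "at least one valid spot urinary UOx:Cr ratio value at baseline" and a valid value between Month 3 and Month 6. The baseline value must exist, but its level is not restricted.

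**Endpoint.** SAP 7.3 gives "the number and associated percent of patients who met each threshold", the thresholds being ULN and 1.5 × ULN, and offers the post-baseline tables as evidence that the drug's effect lasts. For percentage of time, "A patient is considered to have met the threshold if the spot urinary UOx:Cr ratio is" at or below 1.5 × ULN at a post-baseline visit. The descriptive statistics for percentage of time cover only patients who met the threshold at some post-baseline visit.

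**Baseline handling elsewhere.** SAP 7.3 adds a plasma oxalate analysis limited to patients with baseline at or above 1.5 × LLOQ, and shift tables for eGFR categories. SAP 7.4 plans shifts in nephrocalcinosis grade. The urinary thresholds have no counterpart.

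**The concern.** The entry floor (above 1.0 × ULN on two voids) lies below the near-normalization limit (1.5 × ULN), and nothing in the SAP closes that gap. A child who starts at or below 1.5 × ULN and stays there is scored exactly like a child who falls from 4 × ULN. Because the entry rule looks at individual voids while baseline is their mean, the limit at ULN itself has the same weakness.

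With no control arm, the reader has nothing against which to discount such children and will naturally take the percentage as something lumasiran achieved. In a set of about 20 patients, one or two of them shift the figure visibly.

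**Working it through.** The plan states no response rate, power or hypothesis for these endpoints, so there is no figure to reproduce. The check compares the rules, weighs one patient, and asks how often an untreated child would be counted.

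**1. Can an eligible child already be below a limit?** Baseline = (v1 + v2 + v3)/3, in multiples of ULN; eligible if at least two voids exceed 1.0.

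| Voids (× ULN) | Eligible | Baseline mean | ≤1.5 × ULN | ≤ULN |
|---|---|---|---|---|
| 1.4, 1.4, 1.4 | yes | 4.2/3 = 1.40 | yes | no |
| 1.3, 1.4, 1.0 | yes | 3.7/3 = 1.23 | yes | no |
| 1.05, 1.05, 0.6 | yes | 2.7/3 = 0.90 | yes | yes |

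So the gap exists at both limits.

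**2. Weight of one patient.** Planned N = 20 (SAP 5.1): 1/20 = 5.0 points. Primary interim N = 16 (SAP 5.7): 1/16 = 6.25 points.

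**3. How often would an untreated child count?** Assumptions: the child's true ratio stays at R × ULN; voids are lognormal with mean R and s² = ln(1 + CV²); each visit value is the mean of three voids. The documents give no pure void-to-void CV, so 20, 30 and 40% are assumed. There were 400,000 simulated triplicates per cell.

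Probability that one later triplicate mean is ≤1.5 × ULN, given that the entry rule was met and the drug does nothing:

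| True level R | CV 20% | CV 30% | CV 40% |
|---|---|---|---|
| 1.1 | 1.00 | 0.97 | 0.93 |
| 1.3 | 0.90 | 0.82 | 0.77 |
| 1.6 | 0.31 | 0.39 | 0.43 |
| 2.0 | 0.01 | 0.06 | 0.12 |
| 3.0 | 0.00 | 0.00 | 0.00 |

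A child at 1.3 × ULN meets the entry rule with probability 0.97, 0.87 and 0.77 at the three CVs. Once enrolled, that child's expected contribution to the near-normalization rate at any one visit is 0.77 × 5 = 3.9 to 0.90 × 5 = 4.5 points at N = 20.

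As a wider range, SAP Table 3 gives per-patient spot CVs with minimum 13.2% and mean 55.5%. Those come from treated patients in the earlier study and probably include the change on treatment, so the mean overstates void noise. At these two CVs the per-visit probability without drug effect is 0.83 and 0.65 at 1.4 × ULN, and 0.00 and 0.02 at 3 × ULN.

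**4. Effect of restricting the denominator.** Hypothetical: 12 of 20 patients meet 1.5 × ULN at a visit, and k of those 12 were already there at baseline. The rate among patients who could cross is (12 − k)/(20 − k):

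- k = 0: 12/20 = 60.0%
- k = 1: 11/19 = 57.9%
- k = 2: 10/18 = 55.6%
- k = 4: 8/16 = 50.0%

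**The case against.** The endpoint is worded as a state, not a conversion, so an all-patient count is what was specified. It is descriptive, no hypothesis is tested, and the primary endpoint is a percent change that this gap does not touch. Baseline is also not ignored: SAP 6.2 summarises the baseline ratio, SAP 5.2 puts baseline in every listing, spaghetti plots are planned, and SAP 7.1.1 analyses the ratio divided by the age-matched ULN. One sentence in SAP 7.3 and Protocol 7.2.5 speak of counts at visits generally, which could include a baseline row.

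All of that stands and limits the harm. It does not supply the missing number. A summary in mmol/mmol does not show multiples of an age-dependent ULN. SAP 7.1.1 uses published ULNs, whereas SAP 10.4 takes those for the normalization rate from another source. Reading listings is not a pre-specified rate among patients who were able to cross the limit.

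Three stronger readings are tempting, and the documents support none of them:

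- *That the registry data prove such children exist.* SAP 10.2.2 says "All patients except for one patient under 1 year old had spot urinary UOx:Cr ratios above the Matos ULN". This is a single reading from an unselected registry patient, and a child at that level on two of three voids would fail criterion 3. It does not show eligible children between 1.0 and 1.5 × ULN.
- *That the endpoint's ULN is higher than the one used at entry.* SAP 10.4 says "ULNs will be defined in the separate normal range report that will be finalized before database lock". That report is not available, and a lower ULN would shrink the gap.
- *That an untreated child would stay near-normal for most of the study.* The simulation holds the multiple of ULN fixed. The limit is the ULN for age, which falls through early childhood in healthy children (SAP 10.2.1), while SAP 7.1 expects little age-related decline in PH1. On those premises an untreated child drifts above the limit, so the per-visit figures do not carry over to years of follow-up.

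**Conclusion.** The point holds as a gap in definition. Eligible children can have a baseline mean at or below 1.5 × ULN, or even at or below ULN, and SAP 7.3 counts them as meeting the limit whether or not the ratio has changed. Each one counted is worth 5 points at N = 20 and 6.25 at N = 16.

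The total effect cannot be derived, because the documents do not say how many children have mildly raised baselines. Under the stated assumptions (lognormal voids, stable multiple of ULN, CV 20–40%) the per-visit effect is large near 1.3 × ULN and nil by about 3 × ULN. If every baseline is that high, the planned figures are sound, and the extra rows would show it. This is a worthwhile, inexpensive improvement to how secondary endpoints are reported. It does not threaten the primary result.

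**What to change.** In SAP 7.3:

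1. Report the number and percentage of patients at or below ULN and at or below 1.5 × ULN at baseline, using the same ULN table as the endpoint.
2. For each limit, keep the planned all-patient count and add the proportion meeting it among patients whose baseline mean was above that limit.
3. Give percentage of time at or below 1.5 × ULN for all patients with baseline above 1.5 × ULN, entering those who never meet it as 0%. Show this beside the planned descriptive statistics, which cover only patients with at least one post-baseline value meeting the threshold.

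The cost is SAP wording and a few rows in existing tables, with no new data. The downside is a slightly smaller denominator and possibly a lower rate.

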**Table 1: Schedule of Assessments –Primary Analysis Period (Screening through Month 6): All Patients**

*After Month 6, patients with weight <10 kg follow Table 2. Patients with weight ≥10 kg follow Table 4.*

Study Period Study Visit	Notes	Screening	6-Month Primary Analysis Period							
			Baseline	Wk 2	M1	M2	M3	M4	M5	M6
Study Day (±Visit Window)		-60 to -1	1 (±3)	15 (±14)	29 (±14)	57 (±14)	85 (±14)	113 (±14)	141 (±14)	169 (±14)
Study drug dosing in patients <10 kg	Dosing must be at least 21 days apart. Section 5.2.2; Table 7		X		X	X	X	X	X	X
Study drug dosing in patients ≥10 kg			X		X	X	X			X
Blood samples for PK analyses	See Table 5 for blood collection timepoints.		X							X
Blood samples for PD analyses	Collected predose, when applicable. Section 6.3.	X	X		X	X	X	X	X	X
24-hour urine collections for PD analyses	At Screening and Month 6, three collections are performed predose. For patients unable to comply, a single catheterized 24-hour collection may be performed. Section 6.2	X								X
Single-void urine collections for PD analysis (3 collections)	Following screening, 3 single-void collections are collected within 7 days predose (first morning voids are preferred). Section 6.2	X			X	X	X	X	X	X
Blood sample for pyridoxine (vitamin B6) levels	Only in patients receiving therapeutic pyridoxine. Do not collect within 6 hours of pyridoxine dose. Section 5.3	X	X				X			X
Renal stone events	Renal stone events are not considered AEs or SAEs. Section 6.3.3									
Renal ultrasound	Performed as per procedure manual. Section 6.3.4	X								X
Developmental assessment	Vineland Adaptive Behavior Scale. Section 6.7	X								X
Patient/caregiver experience and impact questionnaire	Section 6.8	X								X
ADA sample	Collect predose. Section 6.5.5.1		X		X		X			X

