## 2. OBJECTIVES AND ENDPOINTS

Objectives	Endpoints
Primary	

Evaluate the effect of lumasiran on urinary oxalate excretion

	

Percent change in urinary oxalate excretion from baseline to Month 6

Secondary	
Extension Phase (Month 6 to End of Study) 

Evaluate the long-term effects of lumasiran on urinary oxalate

	Extension Phase (Month 6 to End of Study) 

Percent change in urinary oxalate excretion from baseline

Percentage of time that spot urinary oxalate:creatinine ratio is at or below the near-normalization threshold (<math>\leq 1.5 \times \text{ULN}</math>)

Duration of Study 

Evaluate the effects of lumasiran on additional measures of urinary oxalate

Evaluate the effects of lumasiran on plasma oxalate

Characterize the pharmacokinetics (PK) of lumasiran

Evaluate the effect of lumasiran on renal function

	Duration of Study 

Absolute change in urinary oxalate excretion from baseline

Proportion of patients with urinary oxalate excretion <math>\leq</math> the upper limit of normal (ULN) and <math>\leq 1.5 \times \text{ULN}</math>

Change (percent and absolute) in plasma oxalate from baseline

Plasma PK parameters of lumasiran

Change from baseline in estimated glomerular filtration rate (eGFR)

Exploratory	

Objectives	Endpoints

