3.2. Secondary Endpoints

Extension Phase

- Percent change in urinary oxalate excretion from baseline
- Percentage of time that spot urinary UOx:Cr ratio is at or below the near-normalization threshold ($\leq 1.5 \times \text{ULN}$ for age)

Duration of Study

- Absolute change in urinary oxalate excretion from baseline
- Change (percent and absolute) in plasma oxalate concentration from baseline
- Proportion of patients with urinary oxalate excretion \leq the upper limit of normal (ULN) for age and $\leq 1.5 \times \text{ULN}$ for age
- Plasma PK parameters of lumasiran
- Change in estimated glomerular filtration rate (eGFR) from baseline

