where cumulative months in near-normalization will be defined as the summation across all intervals that met the near-normal threshold and cumulative months of valid assessments will be defined as the summation across all valid post-baseline collections.

Given that the sample collection varies during the study, the calculation of percentage of time will include the following considerations:

- Time will include all follow-up assessments until study end or premature treatment discontinuation, whichever occurs first.
- A linear interpolation method will be used to determine the bookend dates at which the patient crossed into the normal threshold and crossed out of the normal threshold

Descriptive statistics of percentage of time at or below the threshold (among the subset of patients who had at least one post-baseline value that met threshold) will be presented. In addition, the number of patients and associated percentage of patients in each category (e.g. <25%, ≥25% to <50%, ≥50% to <75%, ≥75% of time at or below the threshold) will also be presented.

Descriptive statistics of eGFR at and after 6 months of lumasiran will be presented using the Efficacy Analysis Set and Safety Analysis Set. Shift tables of eGFR categories from baseline to post-baseline visits and an overall worst post-baseline will also be generated

To demonstrate durability of the treatment effect of lumasiran, additional secondary endpoints may be assessed.

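### The Extension Phase endpoint for percentage of time at or below 1.5 × ULN is calculated only over the whole study, so the listed endpoint has no planned estimate

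*SAP*

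**What the plan says.** Protocol Section 2 divides most of the secondary endpoints by period. The percentage of time with the spot ratio at or below 1.5 × ULN stands only under Extension Phase, dated "Month 6 to End of Study", against an objective about long-term effects. SAP 3.2 keeps that grouping and lists "Percentage of time that spot urinary UOx:Cr ratio is at or below the near-normalization threshold" under Extension Phase.

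SAP 4.1 defines the two periods differently. The extension begins after the Month 6 dose; Duration of Study begins at the first dose. It adds: "All data up to the dosing at the Month 6 visit will be included in the Primary Analysis Period".

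In SAP 7.3 the Extension Period paragraph covers percent change in the spot ratio and the 24-hour measures, nothing else. The percentage-of-time calculation comes under Duration of Study (Baseline to End of Study), as the percentage of time that the ratio "is at or below the near-normalization threshold for the duration of study will be summarized". Its denominator "will be defined as the summation across all valid post-baseline collections". Time counts "until study end or premature treatment discontinuation, whichever occurs first", and the dates of crossing the threshold are found by linear interpolation. Descriptive statistics are restricted to patients "among the subset of patients who had at least one post-baseline value that met threshold".

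**The concern.** The endpoint as listed asks what share of time after Month 6 a child stays near-normal. The calculation as written answers another question, because it also counts the months during which the drug is taking effect. A patient who responds slowly and then holds is scored below the listed endpoint. A patient who responds early and then loses control is scored above it.

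The SAP gives no route from one to the other. SAP 1 says that changes to the protocol's methods will be described and justified in Section 8; the table there has no entry for this endpoint. Three things needed to compute the listed endpoint are also unsettled:

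- The start of the clock is not stated for this calculation. It could be Day 1 or the first post-baseline sample.
- A plain filter on the Extension Period would lose the Month 6 sample. Protocol Table 1 says "Following screening, 3 single-void collections are collected within 7 days predose", so that sample belongs to the Primary Analysis Period under SAP 4.1, yet interpolation into the extension has to start from it.
- The subset with at least one value meeting the threshold is defined on the whole study.

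A further consequence follows from the stopping rule. Entry to the Efficacy Analysis Set needs one valid baseline value and one valid value from Month 3 to Month 6. A patient who stops treatment before Month 6 can therefore receive a value for an Extension Phase endpoint with no extension treatment time behind it.

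**Working it through.** The documents give no figure for this endpoint, so there is nothing to reproduce. The check is how far the two definitions can differ.

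**Inputs.** The extension starts at Month 6 and the study ends at Month 60 (Protocol Section 2 and Section 3.3.1). The first scheduled post-baseline spot sample is at Month 1 (Protocol Table 1). The clock therefore starts at Month 0 (Day 1) or Month 1.

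**Formula.** Let *p* be the share of the SAP window before Month 6, *A* the fraction of that early time at or below threshold, and *E* the fraction of extension time at or below threshold.

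- SAP figure = *pA* + (1 − *p*)*E*
- Listed endpoint = *E*
- Difference = *p*(*A* − *E*), which cannot exceed *p* in size because *A* and *E* lie between 0 and 1

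For a window ending at Month *T*, *p* = 5/(*T* − 1) with a Month 1 clock and 6/*T* with a Day 1 clock.

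| Window ends | Month 1 clock | Day 1 clock |
|---|---|---|
| Month 60 | 5/59 = 8.5% | 6/60 = 10.0% |
| Month 36 | 5/35 = 14.3% | 6/36 = 16.7% |
| Month 24 | 5/23 = 21.7% | 6/24 = 25.0% |
| Month 12 | 5/11 = 45.5% | 6/12 = 50.0% |

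Scheduled study days give the same Month 60 values: (169 − 29)/(1681 − 29) = 140/1652 = 8.5%, and (169 − 1)/(1681 − 1) = 168/1680 = 10.0%.

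Windows shorter than Month 60 are assumptions. They arise for a patient who stops treatment at that point, because the clock then stops, or at one of the further interim analyses that SAP 5.7 allows without a date.

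**Two illustrative patients**, with assumed crossings midway between scheduled samples:

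(a) Crosses in at Month 2.5 and holds. Extension-only value: 100%.
- To Month 60: 57.5/59 = 97.5% or 57.5/60 = 95.8%.
- To Month 12: 9.5/11 = 86.4% or 9.5/12 = 79.2%.
- All fall in the top category (≥75%), so the category does not change.

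(b) Crosses in at Month 1.5 and out at Month 7.5, midway between the Month 6 and Month 9 samples at ≥10 kg.
- To Month 60: SAP 6/59 = 10.2% or 6/60 = 10.0%; extension-only 1.5/54 = 2.8%. Same category.
- To Month 24: SAP 6/23 = 26.1% or 6/24 = 25.0%; extension-only 1.5/18 = 8.3%. The patient moves from <25% to the next category up.

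**The case against.** The best defence is that the SAP does not leave the extension unaddressed. SAP 5.2 says that summaries for each period use that period's data, and SAP 4.1 provides for whole-study summaries of secondary endpoints. On that reading only an explicit formula is missing. But neither rule names this endpoint, gives a starting anchor or deals with the interval that straddles Month 6. The closing remark in SAP 7.3, that additional secondary endpoints may be assessed, commits to nothing. What does stand is a limit on the wording: extension data do enter the whole-study ratio, and what is missing is a specified estimate for the extension alone.

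Several other points have force:

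- The lost Month 6 anchor and the whole-study subset are not independent errors. They follow from the single mismatch, and matter because any extension-only version must settle them.
- SAP 4.1 starts Duration of Study at the first dose, which favours a Day 1 clock. The denominator built from post-baseline collections keeps this open.
- The table in SAP Section 8 covers changes from SAP V2.0, so an earlier version may have read the same way. The current SAP 3.2 and 7.3 still disagree.
- The intended window is not certain. The rationale for Amendment 1 calls this an Extension Phase endpoint, but its change description links it to an objective listed under Duration of Study. Correcting the lists could be the right repair.
- The bounds are extremes, the category change needs a particular pattern and window, and the categories are given only as examples.
- The endpoint is descriptive and no formal hypothesis is tested. By-visit proportions, individual plots and listings would still show what happens after Month 6.

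These points limit the consequence. They do not remove the contradiction.

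**Conclusion.** The concern holds. Followed as written, the SAP reports a whole-study quantity for an endpoint that both documents define on the extension, and it records no reason. At full follow-up the error is at most 8.5 to 10.0 percentage points for a patient, reached only if one period is wholly at or below threshold and the other wholly above. It is larger for short windows: up to 21.7 to 25.0 points at Month 24 and 45.5 to 50.0 at Month 12. Interpolation will usually make it smaller.

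The bounds need only the visit schedule and the two possible clock starts. The short windows and the patient examples are assumptions, since the documents give no data for this endpoint. The damage is confined to the value and label of this one endpoint. It should be corrected because the reader would take the figure for long-term control, and because in an open-label study an unresolved window could be chosen after the data are seen.

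**What to change.** In SAP 7.3, move the endpoint to the Extension Period and state that:

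- numerator and denominator run from Month 6 to study end or premature treatment discontinuation;
- the predose Month 6 spot value is the starting anchor for interpolation, although SAP 4.1 assigns it to the Primary Analysis Period;
- the subset with at least one value meeting the threshold is defined on the same window;
- patients with no time after Month 6 are not evaluable for this endpoint, and their number is reported.

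Keep the whole-study percentage as a separately labelled supplementary summary with its clock start stated. If the whole-study window was what the sponsor intended, amend Protocol Section 2 and SAP 3.2 instead and justify the change in SAP Section 8.

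The first route costs some SAP wording and a window, anchor and subset rule in one program. No new data are needed. The drawback is that patients who stop before or soon after Month 6 will have no value, or one that rests on a short window.
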